3. OBJECTIVES AND ENDPOINTS

Table 7 presents the objectives and endpoints.

Table 7: Objectives and Endpoints

Objectives	Endpoints
Primary	
To determine the efficacy of pemigatinib in participants with locally advanced/metastatic or surgically unresectable solid tumor malignancies with an activating FGFR mutation or translocation	
• ORR: defined as the proportion of participants in each cohort who achieve a CR or PR based on RECIST v1.1
Secondary	
• PFS: defined as the time from first dose until PD (per RECIST v1.1 or RANO) or death (whichever is first) in each cohort• DOR: defined as the time from the date of first assessment of CR or PR until the date of the first PD (per RECIST v1.1 or RANO) or death (whichever is first) in each cohort• DCR: defined as the proportion of participants who achieved best overall response of CR, PR, or SD per RECIST v1.1 or RANO• OS: defined as the time from first dose of study drug to death of any cause in each cohort• Safety and tolerability: Occurrence of TEAEs and treatment-related AEs according to NCI CTCAE v5.0, physical exam changes, vital sign changes, laboratory evaluations, and ECG values in each cohort

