4. STUDY DESIGN

4.1. Overall Design

This is an open-label, monotherapy study of pemigatinib in participants with advanced/metastatic or surgically unresectable solid tumor malignancies harboring an activating FGFR mutation or translocation. This study consists of 2 cohorts; Cohort A will enroll participants with FGFR translocations, fusions, and rearrangements, and Cohort B will enroll participants with FGFR mutations. This study will enroll approximately 50 participants. Participants will receive pemigatinib 13.5 mg QD continuously as long as they are receiving benefit and have not met any criteria for study withdrawal. Participants with local laboratory data documenting a gain-of-function FGFR1, FGFR2, or FGFR3 mutation gene rearrangement, or other mutation identified in a CLIA-certified laboratory are eligible. Confirmatory testing through the central genomics laboratory (Tempus, Chicago, IL) will be performed for all participants; however, results from the central genomics laboratory are not required before enrollment. Centralized genomic testing results will allow participants to be assigned to 1 of the following cohorts (see [Appendix C](#) for list of alterations):

- Cohort A: FGFR1-3 in-frame fusions or FGFR2 intron 17 rearrangements
- Cohort B: Known/predicted activating point mutations in FGFR1-3 (excluding kinase domain)

Note that there is no difference in the treatment regimen between the cohorts.

The sponsor may choose to cap enrollment of any one tumor type and/or FGFR alteration in order to allow representation of multiple tumor types and avoid analysis being influenced by any 1 tumor type or due to lack of response in 1 or more tumor subtypes.

A fresh biopsy at baseline (or archival tissue that was collected less than 12 months from date of screening) will be mandatory for participants whose tumors were not previously profiled at the reference lab. On-treatment and end of study biopsies are encouraged for participants with safely accessible lesions. Treatment will start on Day 1. Participants will undergo regular safety assessments during treatment as well as regular efficacy assessments. Participants will be allowed to continue administration in 21-day cycles until documented disease progression or unacceptable toxicity is reported.

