10. STATISTICS

10.1. Sample Size Determination

Overall, the study plans to enroll approximately 50 participants. Assuming ORR is 30%, 50 participants will provide at least 80% power to test the null hypothesis of $ORR \leq 15\%$ using a normal-approximate z test at 1-sided significance level of 0.05.

When a tumor subtype j within each cohort reaches 10 participants (or more), a statistical evaluation for ORR (p_j) within the subtype will be conducted. The tumor subtype j may be discontinued from further enrollment if the posterior probability $P(p_j < 0.15|n_j, N_j, \alpha, \beta) > 0.3$ where n_j is the number of responders in j th subtype, N_j is the number of participants with j th tumor subtype, α and β are parameters of the prior distribution and are set to be $\alpha = 1.7625$ and $\beta = 9.9875$ (Beta distribution with mean = 0.15, variance = 0.01). Tumor subtypes with at least 10 patients and $P(p_j < 0.15|n_j, N_j, \alpha, \beta) \leq 0.3$ may continue to enroll participants. Any tumor subtype j with at least 10 participants and $P(p_j > 0.30|n_j, N_j, \alpha, \beta) > 0.5$ may enroll up to 30 additional participants as an expansion cohort of the tumor subtype. These participants will not be counted towards the 50 participants planned for the study. At the end of the study, $P(p_j < 0.15|n_j, N_j, \alpha, \beta)$ and $P(p_j > 0.30|n_j, N_j, \alpha, \beta)$ will be evaluated for all tumor subtypes within each cohort (see [Table 14](#) and [Table 15](#)). A cohort of at least 25 participants will provide > 0.8 probability of observing 6 responders if underlying response rate is 0.3. The initial calculation of these posterior probabilities of each tumor subtype will begin when 10 participants have completed the assessment for primary response.

These rules based on posterior probabilities are provided as guidance for recruiting participants and discontinuing recruitment due to lack of response. The decision to continue recruiting to a tumor subtype or discontinue recruitment will be made based on the degree of responses observed (eg, number of CRs), other relevant clinical parameters, and medical assessments.

In addition to the aforementioned process, other methods including but not limited to hierarchical Bayesian models may be used to decide if a tumor subtype in each cohort will discontinue enrollment or continue to enroll subjects.

Table 14: $P(p < 0.15 | n/N, \alpha = 1.7625, \beta = 9.9875)$

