10.3. Level of Significance

The overall level of significance is 1-sided 0.05.

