10.4. Statistical Analyses

10.4.1. Primary Analysis

The primary endpoint of the study is ORR. Objective response rate is defined as the proportion of participants who achieved a CR or a PR based on RECIST v1.1 or RANO, as assessed by local radiological review. This analysis will be based on the efficacy evaluation population. Participants who do not have sufficient baseline or on-study response assessment information to be adequately assessed for response status will be included in the denominators in the calculation of ORR. The 90% CI for the ORR will be estimated using the Clopper-Pearson method. The p-value from the exact binomial test will be provided.

The ORR will also be analyzed based on the per protocol population as a sensitivity analysis.

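### The primary endpoint is ORR per cohort in Tables 1 and 7, but the null, the alpha and the 80% power belong to ORR pooled over about 50 participants

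*Protocol*

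**What the plan says.** Table 7 in Section 3, and identically Table 1 in the Protocol Summary, defines the primary endpoint as "ORR: defined as the proportion of participants in each cohort who achieve a CR or PR based on RECIST v1.1". Section 4.1 sets out the cohorts, with point mutations assigned to Cohort B: "This study consists of 2 cohorts; Cohort A will enroll participants with FGFR translocations, fusions, and rearrangements, and Cohort B will enroll participants with FGFR" (quoted in part). No cohort sizes or allocation are given.

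The inferential statements are made at a different level:

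- Section 10.1: "Overall, the study plans to enroll approximately 50 participants". It continues: "Assuming ORR is 30%, 50 participants will provide at least 80% power to test the null hypothesis of" ORR at or below 15%, by a normal-approximation z test at 1-sided 0.05.
- Section 10.3: "The overall level of significance is 1-sided 0.05". There is no division between cohorts.
- Section 10.4.1: "Objective response rate is defined as the proportion of participants who achieved a CR or a PR based on RECIST v1.1 or RANO", with no reference to cohorts, and then "The p-value from the exact binomial test will be provided".

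Section 10.1 contains one figure for a single cohort: with at least 25 participants, the probability of observing 6 responders exceeds 0.8 at a true rate of 0.3. No null rate or significance level is attached to it.

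**The concern.** The protocol fixes the primary endpoint, the hypothesis, the alpha and the power, but for two different quantities. This cannot be left to the SAP: whichever reading an SAP adopts, it departs from one part of the protocol.

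What is at stake is what counts as success. If the tables govern, there are two primary conclusions, the 80% applies to neither, and nothing is said about how one 0.05 covers two tests. If Section 10 governs, the tables misstate the primary endpoint and cohort results are estimates only. In an open-label, single-arm trial with locally assessed response, the choice between one pooled claim and two cohort claims should not remain open until results are known.

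**Working it through.** **Inputs.** p0 = 0.15, p1 = 0.30, 1-sided alpha = 0.05, N = 50 (Sections 10.1 and 10.3). The z test is named in Section 10.1 and the exact binomial test in Section 10.4.1. Cohort size n is my assumption throughout.

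**Formulas.**

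- z test: power = Φ{[p1 − p0 − 1.645·√(p0(1−p0)/n)] / √(p1(1−p1)/n)}.
- Exact test: find the smallest c with P(X ≥ c | n, 0.15) ≤ 0.05; power = P(X ≥ c | n, 0.30).

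**Step 1: reproduce the plan's figure (pooled, n = 50).** √(0.15·0.85/50) = 0.0505 and √(0.30·0.70/50) = 0.0648. Power = Φ[(0.15 − 1.645·0.0505)/0.0648] = Φ(1.03) = 84.9%. The claim of at least 80% is correct for pooled ORR by the z test. By the exact test, c = 13, actual alpha is 0.030 and power is 77.7%.

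**Step 2: the same test within one cohort.** For n = 25 by the z test: Φ[(0.15 − 1.645·0.0714)/0.0917] = 63.9%.

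| n in cohort (assumed) | z test | Exact c | Exact alpha | Exact power |
|---|---|---|---|---|
| 15 | 49.4% | 6 | 0.017 | 27.8% |
| 23 | 61.3% | 7 | 0.046 | 56.0% |
| 25 | 63.9% | 8 | 0.025 | 48.8% |
| 27 | 66.2% | 8 | 0.040 | 58.9% |
| 35 | 74.4% | 10 | 0.029 | 63.5% |
| 40 | 78.5% | 11 | 0.030 | 69.1% |

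Exact power is saw-toothed, and 15, 25, 35 and 40 lie just past a drop. Nearby sizes do better (n = 14: 41.6%; n = 33: 69.6%; n = 38: 74.5%), but all stay below 80%.

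**Step 3: can any split of 50 work?** A cohort first reaches 80% at n = 43 by the z test and n = 48 by the exact test, leaving 7 or 2 participants for the other cohort. Over splits k/(50 − k) with k from 5 to 45, the lower of the two powers is at most 63.9% by the z test (25/25) and 56.0% by the exact test (27/23).

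**Step 4: the 25-participant sentence.** P(X ≥ 6 | 25, 0.30) = 80.7%, which reproduces the figure of more than 0.8. But P(X ≥ 6 | 25, 0.15) = 16.2%, so 6 of 25 used as a success rule would not meet 1-sided 0.05.

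**Step 5: error rate if each cohort were tested at an undivided 0.05.** With independent cohorts, both truly at 15%, the error is 1 − (1 − a1)(1 − a2). Nominally this is 1 − 0.95² = 9.75%. With the actual exact alphas it is 5.0% at 25/25 and 8.4% at 27/23.

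**The case against.** The strongest reply is that the pooled intent is clear enough. The primary objective in Table 7 covers mutation or translocation together, and Sections 10.1, 10.3 and 10.4.1 all work at study level. Section 10.4.2 specifies the cohort level for DCR, so the authors say so when they mean it. In the tables the cohort phrase also follows PFS, DOR, OS and safety, none of which carries a hypothesis, so it may only describe how results are reported. On that reading the power claim stands and two table entries need correcting.

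That is a good argument for which reading to adopt, and the fix below adopts it. It does not remove the contradiction: both endpoint tables still define the primary endpoint at cohort level.

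Other parts of the design do not rescue cohort-level power. The sentence on 25 participants is not a test against 15% (Step 4). Expansion participants are optional, are recruited by tumor subtype and do not count toward the 50. The Bayesian rules concern tumor subtypes and are described as recruitment guidance.

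Two further criticisms are fair:

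- Enrollment is only approximately 50, and exact power moves with small changes: 81.9% at 48, 75.0% at 49, 77.7% at 50, 80.2% at 51 and 82.5% at 52. Any stated exact power must be tied to its n.
- The z-versus-exact difference and the absence of RANO from the primary endpoint in the tables are separate points. They come up here only because the same sentences have to be rewritten.

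**Conclusion.** The concern holds. The stated hypothesis, alpha and power describe pooled ORR, while Tables 1 and 7 make ORR in each of two cohorts the primary endpoint. The arithmetic behind the 80% is sound, but it is attached to a different quantity.

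At the protocol's own rates and alpha, a cohort of 25 has 63.9% (z) or 48.8% (exact) power. These per-cohort figures depend on an assumed size. The conclusion does not: no division of 50 gives both cohorts 80%. It should be corrected before the analysis, because it decides what the trial's primary conclusion is about.

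**What to change.** 1. In Tables 1 and 7 and Section 10.4.1, name pooled ORR (RECIST v1.1 or RANO) in the planned 50 participants as the single confirmatory endpoint, tested by the exact binomial test against 15% at 1-sided 0.05.
2. Report ORR by cohort as estimates with 90% Clopper-Pearson intervals and no success claim.
3. In Section 10.1, give the power of the test that will be used: at n = 50 the exact test rejects at 13 or more responders with 77.7% power, against 84.9% by the z test. Say that both the cut-off and the power change if the final number differs from 50.
4. Only if a confirmatory test in each cohort is intended, state instead the cohort sizes, the power of each and how the 0.05 is divided. For 80% power in each at an undivided 0.05, the z test needs 43 per cohort (86 in total) and the exact test first reaches it at 48 per cohort (96 in total). Dividing the alpha would raise these numbers.

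Items 1 to 3 change text only, with no new visits, data or participants. Because they restate the primary endpoint, they do need a protocol amendment. Cohort results become descriptive, and the stated pooled power falls slightly below 80%.

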4. STUDY DESIGN

4.1. Overall Design

This is an open-label, monotherapy study of pemigatinib in participants with advanced/metastatic or surgically unresectable solid tumor malignancies harboring an activating FGFR mutation or translocation. This study consists of 2 cohorts; Cohort A will enroll participants with FGFR translocations, fusions, and rearrangements, and Cohort B will enroll participants with FGFR mutations. This study will enroll approximately 50 participants. Participants will receive pemigatinib 13.5 mg QD continuously as long as they are receiving benefit and have not met any criteria for study withdrawal. Participants with local laboratory data documenting a gain-of-function FGFR1, FGFR2, or FGFR3 mutation gene rearrangement, or other mutation identified in a CLIA-certified laboratory are eligible. Confirmatory testing through the central genomics laboratory (Tempus, Chicago, IL) will be performed for all participants; however, results from the central genomics laboratory are not required before enrollment. Centralized genomic testing results will allow participants to be assigned to 1 of the following cohorts (see [Appendix C](#) for list of alterations):

- Cohort A: FGFR1-3 in-frame fusions or FGFR2 intron 17 rearrangements
- Cohort B: Known/predicted activating point mutations in FGFR1-3 (excluding kinase domain)

Note that there is no difference in the treatment regimen between the cohorts.

The sponsor may choose to cap enrollment of any one tumor type and/or FGFR alteration in order to allow representation of multiple tumor types and avoid analysis being influenced by any 1 tumor type or due to lack of response in 1 or more tumor subtypes.

A fresh biopsy at baseline (or archival tissue that was collected less than 12 months from date of screening) will be mandatory for participants whose tumors were not previously profiled at the reference lab. On-treatment and end of study biopsies are encouraged for participants with safely accessible lesions. Treatment will start on Day 1. Participants will undergo regular safety assessments during treatment as well as regular efficacy assessments. Participants will be allowed to continue administration in 21-day cycles until documented disease progression or unacceptable toxicity is reported.

4.2. Overall Study Duration

The study begins when the first participant signs the ICF. The end of the study is defined as the date of the last visit of the last participant in the study.

Once the study has reached the target enrollment, if there are approximately ≤ 3 participants on study for more than 6 months, a database lock of the study may occur to allow the analysis of the study data. Any remaining participants may continue to receive study treatment and be seen by the investigator per Protocol. The investigator will be expected to monitor for and report any SAEs, AEs of special interest, and pregnancies, as detailed in Section 9. The remaining

participants are considered to be on study until a discontinuation criterion is met and written notification is provided to the sponsor.

4.3. Study Termination

The investigator retains the right to terminate study participation at any time, according to the terms specified in the study contract. The investigator is to notify the IRB/IEC in writing of the study's completion or early termination, send a copy of the notification to the sponsor or sponsor's designee, and retain 1 copy for the site study regulatory file.

The sponsor may terminate the study electively, if required by regulatory decision. If the study is terminated prematurely, the sponsor will notify the investigators, the IRBs and IECs, and regulatory bodies of the decision and reason for termination of the study.

5. STUDY POPULATION

Deviations from eligibility criteria are not allowed because they can potentially jeopardize the scientific integrity of the study, regulatory acceptability, and/or participant safety. Therefore, adherence to the criteria as specified in the Protocol is essential. Prospective approval of Protocol deviations to recruitment and enrollment criteria, also known as Protocol waivers or exemptions, are not permitted.

5.1. Inclusion Criteria

Participants are eligible to be included in the study only if all of the following criteria apply:

1. Ability of the participant (or parent, guardian, or legally authorized representative) to comprehend and willingness to sign the ICF.
2. Age 18 years or older, inclusive at the time of signing the informed consent.
3. Histologically or cytologically confirmed solid tumor malignancy that is advanced or metastatic (Stage IIIB or IV per the [American Joint Committee on Cancer, Cancer Staging Manual, 6th Edition](#)) or is surgically unresectable.
4. Radiographically measurable disease (per RECIST v1.1 or RANO for primary brain tumors). Tumor lesions located in a previously irradiated area or in an area subjected to other loco-regional therapy are considered measureable if progression has been clearly demonstrated in the lesion.
5. Documentation of an FGFR1-3 gene mutation or translocation (see Section [8.4](#) and [Appendix C](#)).
6. Objective disease progression after at least 1 prior therapy, and there is no further approved therapy available that is likely to provide clinical benefit. Participants who are intolerant to or decline the approved therapy are eligible only if they have no therapy available that is likely to provide clinical benefit.
7. ECOG performance status 0 to 2.

8. Baseline archival tumor specimen (if less than 12 months from date of screening) available or willingness to undergo a pretreatment tumor biopsy to obtain the specimen. Must be a tumor block or approximately 15 unstained slides from biopsy or resection of primary tumor or metastasis.
9. Not eligible or able to participate in any other Incyte Sponsored Clinical Trial.
10. Willingness to avoid pregnancy or fathering children based on the criteria below.
 - a. Men must agree to take appropriate precautions to avoid fathering children (with at least 99% certainty) from screening through 90 days after the last dose of study drug and must refrain from donating sperm during this period. Permitted methods that are at least 99% effective in preventing pregnancy (see [Appendix A](#)) should be communicated to the participants and their understanding confirmed.
 - b. Women of childbearing potential must have a negative serum pregnancy test at screening and before the first dose on Day 1 and must agree to take appropriate precautions to avoid pregnancy (with at least 99% certainty) from screening through safety follow-up. Permitted methods that are at least 99% effective in preventing pregnancy (see [Appendix A](#)) should be communicated to the participants and their understanding confirmed.
 - c. Women of nonchildbearing potential (ie, surgically sterile with a hysterectomy and/or bilateral oophorectomy OR ≥ 12 months of amenorrhea) are eligible.

10. Known additional malignancy that is progressing or requires active treatment. Exceptions include basal cell carcinoma of the skin, squamous cell carcinoma of the skin, or in situ cervical cancer that has undergone potentially curative therapy.
11. Participants with laboratory values at screening defined in [Table 8](#).

Table 8: Exclusionary Laboratory Values

Laboratory Parameter	Exclusion Criterion
Hematology	
a	Platelets $\leq 75 \times 10^9/L$ (transfusion allowed with 2-week washout period)
b	Hemoglobin $\leq 9.0 \text{ g/L}$ (transfusion allowed within 2-week washout period)
c	Absolute neutrophil count $\leq 1.5 \times 10^9/L$
Hepatic	
d	ALT $\geq 3 \times \text{ULN}$
e	AST $\geq 3 \times \text{ULN}$ ($5 \times \text{ULN}$ for liver mets)
f	Total bilirubin $\geq 1.5 \times \text{ULN}$ ($2.5 \times \text{ULN}$ if Gilbert's syndrome or liver mets)
g	Alkaline phosphatase $\geq 3 \times \text{ULN}$
Renal	
h	Serum creatinine clearance $\leq 30 \text{ mL/minute}$ based on Cockcroft-Gault formula
Chemistry	
i	Serum phosphate $> \text{ULN}$
j	Serum calcium Outside of normal range or serum albumin-corrected calcium outside of the normal range when serum albumin is outside of the normal range

12. History of calcium and phosphate hemostasis disorder or systemic mineral imbalance with ectopic calcification of soft tissues (exception: commonly observed calcifications in soft tissues such as the skin, kidney tendon or vessels due to injury, disease, or aging in the absence of systemic mineral imbalance).
13. Gastrointestinal condition/disorder that may raise gastric and/or small intestinal pH that could interfere with absorption, metabolism, or excretion of pemigatinib.
14. Inability to swallow and retain oral medication.
15. Clinically significant or uncontrolled cardiac disease including unstable angina, acute myocardial infarction within 6 months from Day 1 of study drug administration, New York Heart Association Class III or IV congestive heart failure, and uncontrolled arrhythmia (participants with a pacemaker or with atrial fibrillation and well-controlled heart rate are allowed).
16. History or presence of an abnormal ECG that, in the investigator's opinion, is clinically meaningful. A screening QTcF interval > 480 milliseconds is excluded. For participants with an intraventricular conduction delay (QRS interval ≥ 120 milliseconds), the JTc interval may be used in place of the QTc with sponsor approval. The JTc must be ≤ 340 milliseconds if JTc is used in place of the QTc.
17. Active chronic or current infectious disease requiring systemic antibiotic, antifungal, or antiviral treatment within 2 weeks before enrollment (participants with asymptomatic chronic infections on prophylactic treatment are allowed).
18. Evidence of active HBV or HCV infection (defined as participants with elevated transaminases or cirrhosis. Participants with chronic HBV/HCV infection with no cirrhosis and no elevated transaminases are allowed).
19. Known HIV infection.
20. Current use of prohibited medication as described in Section [6.6.2](#).
21. Use of any potent CYP3A4 inhibitors or inducers or moderate CYP3A4 inducers within 14 days or 5 half-lives (whichever is longer) before the first dose of study drug.
22. Known hypersensitivity or severe reaction to pemigatinib or excipients of pemigatinib (refer to the [IB](#)).
23. Inability or unlikelihood of the participant to comply with the dose schedule and study evaluations, in the opinion of the investigator.
24. Inadequate recovery from toxicity and/or complications from a major surgery before starting therapy.
25. Women who are pregnant or breastfeeding.
26. Any condition that would, in the investigator's judgment, interfere with full participation in the study, including administration of study drug/treatment and attending required study visits; pose a significant risk to the participant; or interfere with interpretation of study data.
27. History of hypovitaminosis D requiring supraphysiologic doses (eg, 50,000 IU/week) to replenish the deficiency. Vitamin D supplements are allowed.

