2.2.2. Justification for Dose and Regimen

Pemigatinib will be administered at 13.5 mg QD, continuously, during a cycle. Each cycle is 3 weeks. This dose and dosing schedule was selected based on emerging clinical and safety data from the INCB 54828-101 study, where the continuous dosing regimen has been tested in 8 and 16 participants at 9 mg and 13.5 mg QD continuous administration, respectively. In Study INCB 54828-101, the emerging safety data demonstrated that tolerability of the continuous dosing regimen of pemigatinib was comparable to that of intermittent dosing.

The hypothesis with a targeted therapy is that continued inhibition of the aberrant receptor may increase the potential for benefit from the treatment. Therefore, administering pemigatinib continuously will allow that consistent inhibition of the aberrant FGFR receptor in this population. Continuous dosing would still allow for dose holds for safety reasons with criteria and procedures for dose interruptions and adjustments clearly outlined in the Protocol.

Hyperphosphatemia is an expected on-target pharmacological effect of FGFR inhibition. The incidence of hyperphosphatemia, defined as any postbaseline phosphate level exceeding 5.5 mg/dL, has been observed in the majority of participants treated with pemigatinib (refer to the [IB](#) for complete data). Some participants do not achieve hyperphosphatemia, and it is estimated that pharmacological concentration of pemigatinib in these participants is lower (see [Figure 2](#)). Therefore, up-titration of pemigatinib will be used to increase the exposure of pemigatinib in participants who do not achieve hyperphosphatemia when treated with 13.5 mg QD. The goal is to increase the serum concentration of pemigatinib.

Any participant who does not reach the target serum phosphate level of > 5.5 mg/dL at any time during Cycle 1, and who is compliant with taking study drug and does not experience an ongoing Grade 2 or higher treatment-related AEs, will increase the daily dose to 18 mg starting at Cycle 2 Day 1.

Dose modifications for tolerability issues are noted in Section 6.5.

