2.3. Benefit/Risk Assessment of Pemigatinib

Targeted therapies with a manageable safety profile that can provide a durable response or significant disease control in a molecularly defined population would provide a meaningful clinical benefit.

The comprehensive safety data that are included in the **IB** (v5) utilized a data cut of 25 NOV 2018. As of the cutoff date, a total of 562 participants (78 healthy participants and 484 participants with advanced malignancies) were enrolled in ongoing clinical studies and received at least 1 dose of pemigatinib. Based on preliminary unaudited data from these ongoing studies the most frequently occurring TEAEs (ie, incidence > 20%) were (in descending order of

frequency) hyperphosphatemia, diarrhea, alopecia, fatigue, dry mouth, stomatitis, constipation, dysgeusia, nausea, decreased appetite, and anemia. Additional details are provided in the following section.

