8.3.4. Electrocardiograms

Single 12-lead ECGs will be obtained as outlined in the SoA (see [Table 3](#)) using an ECG machine that automatically calculates the heart rate and measures PR, QRS, QT, and QTc intervals. All 12-lead ECGs will be performed with the participant in a recumbent or semirecumbent position after approximately 5 minutes of rest.

The 12-lead ECGs will be interpreted by the investigator at the site to be used for immediate participant management. Additional 12-lead ECGs may be performed as clinically indicated to manage participant safety. The decision to include or exclude a participant or withdraw a participant from the study treatment based on an ECG flagged as "Abnormal, Clinically Significant" is the responsibility of the investigator, in consultation with the sponsor's medical monitor, as appropriate. Clinically notable abnormalities that are considered clinically significant in the judgment of the investigator are to be reported as AEs. In the event that a single QTc is > 480 milliseconds at screening, the participant may enroll if the average QTc for the 3 ECGs is ≤ 480 milliseconds or with approval from the medical monitor. For participants with an intraventricular conduction delay (QRS interval > 120 milliseconds) at screening, the JTc interval may be used in place of the QTc with medical monitor approval. The JTc must be ≤ 340 milliseconds if JTc is used in place of the QTc. In addition, the JTc interval should be used for all subsequent assessments.

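### The hemoglobin exclusion is printed as 9.0 g/L and so excludes no realistic candidate, and Section 8.3.4 allows a monitor-approved QTc above 480 ms that exclusion 16 rules out

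*Protocol*

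**What the plan says.** **Hemoglobin.** Exclusion 11 (Section 5.2) bars "Participants with laboratory values at screening defined in" Table 8. Row b of that table reads "Hemoglobin $\leq 9.0 \text{ g/L}$ (transfusion allowed within 2-week washout period". The platelet row directly above it words its transfusion allowance differently: "transfusion allowed with 2-week washout period". No other section gives a hemoglobin limit.

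**QTc.** Exclusion 16 states: "A screening QTcF interval > 480 milliseconds is excluded". Its only alternative is to use JTc, with sponsor approval, when QRS is at least 120 ms. Section 8.3.4 first says "Single 12-lead ECGs will be obtained as outlined in the SoA". It then provides that, when a single screening QTc exceeds 480 ms, "the participant may enroll if the average QTc for the 3 ECGs is ≤ 480 milliseconds or with approval from the medical monitor". It allows JTc when QRS is strictly above 120 ms.

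**Governing text.** The opening of Section 5 says that deviations from eligibility criteria are not allowed and that waivers or exemptions from enrollment criteria are not permitted.

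**The concern.** Both passages decide who may be dosed, and neither works as printed.

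A hemoglobin limit of 0.9 g/dL screens out nobody who could be ECOG 0 to 2. The protocol then has no working numeric limit, and sites must supply the unit themselves. A working limit matters here. Section 2.3 closes its list of adverse events with incidence above 20% with "dysgeusia, nausea, decreased appetite, and anemia", and Table 6 reports anemia in Study INCB 54828-101. No causal claim is made from these rates.

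For QTc, a participant above 480 ms with medical monitor approval is excluded by one section and enrollable under another. The same enrollment would be a protocol deviation at one site and compliant at another. The approval route has no ceiling, so Section 8.3.4 sets no limit on how prolonged the interval may be at entry.

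**Working it through.** No sample-size or power figure is involved. The check is a unit conversion and a side-by-side reading.

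**1. Hemoglobin (input: 9.0 g/L, Table 8 row b)**

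- As printed: g/L ÷ 10 = g/dL, so 9.0 ÷ 10 = 0.9 g/dL.
- If 9.0 g/dL was intended: 9.0 × 10 = 90 g/L.
- Ratio of intended to printed limit: 90 ÷ 9 = 10.
- Values that pass row b but would fail the inferred limit: above 9 and up to 90 g/L.

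The text reviewed was machine-read from a PDF, so a misread unit is possible. Against that, deciliter units are rendered correctly elsewhere, for example "defined as any postbaseline phosphate level exceeding 5.5 mg/dL" in Section 2.2.2 and throughout Table 11. This makes a misread less likely but does not rule it out.

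Anemia in Table 6: 22/106 = 20.8% on monotherapy overall, and 2/16 = 12.5% on 13.5 mg continuous, the starting regimen of this trial.

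**2. QTc (inputs: exclusion 16, Section 8.3.4, Section 5)**

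| First screening QTc above 480 ms, and | Exclusion 16 | Section 8.3.4 |
|---|---|---|
| Mean of 3 ECGs ≤ 480 ms | Excluded on the single value; eligible if the mean is taken as the screening value | May enroll |
| Mean above 480 ms, no approval | Excluded | May not enroll |
| Mean above 480 ms, monitor approves | Excluded | May enroll |

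The first row can be reconciled: averaging can be read as saying how the screening value is measured. The second row agrees. The third row cannot be reconciled, because the two routes in Section 8.3.4 are joined by *or*, so approval suffices alone.

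An illustration with values that are not from the documents: ECGs of 490, 470 and 495 ms give (490 + 470 + 495)/3 = 1455/3 = 485 ms. The average fails 480 ms, exclusion 16 excludes, and Section 8.3.4 still allows enrollment on approval.

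Two features of the protocol favor exclusion 16 as the controlling text. Section 5 forbids waivers of enrollment criteria. And where discretion is wanted, it is written into the criterion itself: exclusion 8 names medical monitor approval twice, and exclusion 16 names sponsor approval for JTc. It gives none for QTcF above 480 ms.

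Section 8.3.4 also schedules single ECGs and then refers to three, without saying when the other two are taken. The JTc trigger differs between the two sections only at a QRS of exactly 120 ms.

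**The case against.** The strongest reply is that the hemoglobin entry is an obvious slip. A limit of 0.9 g/dL is so implausible that most sites would read g/dL, and the page has not been checked against the source. Other text also helps. Exclusion 4 requires recovery to Grade 1 or lower from adverse events of previous therapies, and inclusion 6 requires at least one such therapy, so much treatment-related anemia is caught. Exclusion 26 lets the investigator bar anyone at significant risk. This stands as a reason not to dramatize the point. It does not repair the row: disease-related anemia falls outside exclusion 4, exclusion 26 is judgment, and a binding threshold should not depend on readers correcting its unit.

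On QTc, it can be said that Section 5 already settles the matter in favor of exclusion 16. That is the better reading of intent, but it leaves in place a clause in Section 8.3.4 that tells sites the opposite.

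Three stronger readings are tempting and are not supported:

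- **That severely anemic participants would be enrolled.** Nothing shows this is likely, and the anemia rate on the 13.5 mg continuous regimen (12.5%) is below the overall rate (20.8%).
- **That participants above 500 ms would enter.** The clause has no cap, so it does not literally forbid this. But a monitor would have to approve a value at which Section 6.5.4 requires stopping drug and hospitalization. The investigator would also have to judge the ECG not clinically meaningful under exclusion 16. The scenario is remote.
- **That the repeat-once rule in Section 8.1.2 is a further contradiction.** It applies only when the investigator believes a result is in error, and Section 8.3.4 can be read as the more specific rule for ECGs.

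**Conclusion.** Both points hold and should be fixed. As printed, the protocol's only numeric hemoglobin limit is 0.9 g/dL and excludes no realistic candidate; it is 10 times too low if 9.0 g/dL was intended. That rests on three things: the source page matching the extracted text, the inference that g/dL was meant, and general clinical knowledge that an ECOG 0 to 2 candidate would not have such a value.

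The QTc contradiction is confined to the medical monitor route: excluded under exclusion 16, enrollable without an upper limit under Section 8.3.4, and at odds with the no-waiver statement in Section 5. The averaging route is not at fault. The protocol gives no data on how often the conflict would arise.

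The differences over *with* and *within* a washout and over the QRS threshold are minor and are worth aligning only because the same lines are being edited. Exclusion 15, the investigator-opinion part of exclusion 16 and exclusion 26 are partial safeguards meanwhile. A reader might infer that the trial's conclusions are at risk; they are not, since neither point touches sample size, power or the ORR analysis.

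**What to change.** 1. Check Table 8 row b on the source page. If it reads g/L, change the limit to ≤ 9.0 g/dL (90 g/L), once the sponsor confirms the intent, and word the transfusion allowance as in row a, *with* a 2-week washout.
2. Put one QTc rule in exclusion 16: if the first screening QTcF is above 480 ms, two further ECGs are taken and the mean QTcF of the three must be ≤ 480 ms.
3. Delete the medical monitor clause from Section 8.3.4 and have that section refer to exclusion 16. If the sponsor does want discretion, it belongs in exclusion 16 itself, with a cap below the 500 ms stopping level in Section 6.5.4.
4. Use the same QRS threshold (≥ 120 ms) in both places.

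Cost: a few words in Table 8, exclusion 16 and Section 8.3.4. At most two extra screening ECGs are needed, only for participants whose first value exceeds 480 ms, and Section 8.3.4 already implies them. No analysis changes.
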